We propose a randomized crossover study to compare active versus sham RIC combined with one bout of isometric hand exercise. Participants will be randomly assigned the order of the two experimental sessions: active or sham RIC. The isometric hand exercise will be performed in both sessions. The washout period between the two experimental sessions will be two to three weeks to prevent any carry-over effects. Figure 1 outlines the experimental protocol. Each session will consist of a pre-test measurement (baseline), active/sham RIC, post-RIC measurement, an isometric hand exercise and a post-exercise measurement. The total time in each session is around 3 hours including preparation. At the beginning and end of active/sham RIC, blood samples will be collected to measure changes in inflammatory mediators.

[figure not shown]

Figure 1. The experimental protocol.

Participants with chronic cSCI (n=8, ASIA Impairment Scale (AIS) A-D) and age-matched (within ± 5 years) able-bodied controls (n=8) will be recruited. Participants with cSCI must have at least partial ability to make volitional finger opposition movements (thumb and index finger) in at least one hand. Participants will be excluded if they have concurrent serious medical illness, traumatic brain injury, cardiovascular or pulmonary complications, seizure history, deep vein thrombosis, or any other issues that would increase risk of magnetic or electrical stimulation required for outcome measure assessment. We will also document medications that participants are currently using for systemic inflammation, spasticity, anxiety, or depression, which could affect nervous system excitability. One screening session will be conducted to confirm eligibility and determine the target arm in each participant. The arm with consistent responses on abductor pollicis brevis muscle (APB) induced by magnetic or electrical stimulation will be the target arm. Transcranial magnetic stimulation (TMS) will be performed to determine each subject's optimal scalp location for hand motor cortex stimulation, and to determine resting motor threshold for the APB muscle. Participants will be withdrawn if TMS-induced motor evoked potentials (MEPs) are unable to be detected at the APB muscles on either hand at stimulus intensity below 90% of maximal stimulator output. More details regarding inclusion and exclusion criteria are listed in the human subject section.

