The primary muscles assessed in this study are APB and the first dorsal interosseous (FDI) muscle on the target arm. The electrophysiological variables include intra-cortical facilitation/inhibition, corticospinal excitability and peripheral nerve conduction profile. Electrophysiological variables will be measured at pre-test measurement (baseline), post-RIC measurement (post-RIC), and post-exercise measurement (immediately after the isometric hand exercise (post-RICx-0) and 15 minute later (post-RICx-15)). The blood samples will be collected at baseline and post-RIC to measure gene expression for inflammatory mediators related to Toll-like receptor (TLR) signal pathway.

For the isometric hand exercise, subjects will be instructed to pinch a dynamometer (Anyload) with thumb and index finger at different intensities and durations. Performing volitional movements at varying intensities stimulates corticospinal circuits^{42,43}. The intensities of pinch force will be 10%, 25%, and 50% of the maximal voluntary contraction (MVC). For each intensity, durations of 2, 4, and 6 s will be employed, which resulted in nine different combinations delivered in pseudorandom order. Participants will perform 2 sets of the isometric hand exercise (18 pinches in total). The interval between each pinch will be 2 seconds, with 30 second intervals between each set.

Aim 1: To determine the effects of active versus sham RIC prior to one bout of muscle contraction exercise on motor corticospinal excitability.

Hypothesis 1A: Motor evoked potential (MEP) amplitudes at the APB muscle (Primary Outcome) will significantly increase after active RIC plus isometric hand exercise compared to sham RIC plus isometric hand exercise. Active RIC alone will not significantly increase motor evoked potential amplitudes. These trends will be similar in both cSCI and able-bodied participants.

Hypothesis 1B: Secondary electrophysiological outcomes at the APB muscle will significantly change after active RIC plus isometric hand exercise compared to sham RIC plus isometric hand exercise. Short-interval and long-interval cortical inhibition will decrease; intracortical facilitation will increase. Active RIC alone will not significantly change these outcome measures. These trends will be similar in both cSCI and able-bodied participants.

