We hypothesize that RIC might synergize with motor task learning via increased corticospinal excitability at supraspinal level. In order to test our hypothesis, we select an isometric hand exercise as the motor training task in this pilot study. The reason is that several studies have demonstrated immediate and transient increased MEPs as a result of post-exercise facilitation in able-bodied participants after a short period of repetitive contraction exercise in thenar muscle⁴⁴, wrist muscle⁴⁵, forearm⁴⁶ and leg^{47,48}. Additionally, the various combinations of the intensity and the duration of pinch movements in our study, as well as the use of an intrinsic hand muscle, theoretically involves more cortical attention, which should magnify the likelihood of supraspinal neuroplasticity^{42,43,49}. We will test MEPs at baseline, post-RIC, post-RICx-0 and post-RICx-15. We expect to observe further increased MEPs of the APB thenar muscle at post-RICx due to the synergistic effects of active RIC on isometric hand exercise compared to sham RIC. Likewise, we expect that intracortical inhibition and intracortical facilitation of the APB muscle will decrease and increase, respectively. We also anticipate similar responses of all electrophysiological outcomes in both participants with cSCI and able-bodied participants.

Method: We will conduct electrophysiological measurements at four time points: baseline, post-RIC, post-RICx-0 and post-RIC-15. The post-RIC measurement allows us to first observe whether RIC-alone acutely affects corticospinal excitability. In addition, the 15-minute follow-up measurements (post-RICx-15) will allow us to investigate if the exercise effects will last longer due to active versus sham RIC. In order to localize changes on the pathway from the motor cortex to muscle, the electrophysiological outcomes include changes of intra-cortical facilitation/inhibition, peak-to-peak amplitude of MEPs at 120% resting motor threshold (RMT), and peripheral nerve profile including M/F waves. We have and already use all the major equipment necessary for outcome assessments, including a MagPro X100 TMS system (MagVenture), Digitimer peripheral nerve stimulators (Digitimer), surface EMG pre-amplifiers (Motion Lab Systems), and data acquisition boards (National Instruments).

Peak-to-Peak Amplitude of Motor Evoked Potentials at 120% intensity of Resting Motor Threshold (MEP₁₂₀):

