Statistical Analysis: Electrophysiological outcomes will be compared after RIC and after the isometric hand exercise relative to baseline values. Descriptive analysis will be computed first for all outcomes variables to test the distribution of the data and correlation tests will be performed to check the independence among the outcome variables. A three way 2 (cSCI, able-bodied) by 2 (RIC, sham) by 3 (post-RIC, post-RICx-0, post-RICx-15) mixed-ANOVA will be used to analyze MEP₁₂₀ and intra-cortical facilitation/inhibition. If the data is not normally distributed and the assumptions of the ANOVA are not met, Wilcoxon signed rank tests will be used instead. Post hoc pairwise comparisons will be performed using the Bonferroni adjustment, if there are any main or interaction effects within the three independent variables (group, active/sham RIC and time points).

Potential Pitfalls/Alternative approaches/Future Directions: Applying RIC on motor task learning is relatively new area with little preliminary data – therefore, our primary hypothesis that RIC may promote motor task learning via increasing corticospinal excitability is highly speculative. Additionally, the effects of RIC and acute post-exercise facilitation have mostly been shown in able-bodied participants, and there are no published data in the SCI population that measured corticospinal excitability as a mechanism for acute post-exercise facilitation. Therefore, individuals with SCI might demonstrate uncertain responses toward RIC and the isometric hand exercise than that exhibited in able-bodied participants. The inconsistent injury level and the residual nerve circuits among participants with cSCI might result in the wide variability of the outcomes. Nevertheless, although our hypotheses are speculative, the proposed study is designed to provide clear answers via observing the responses in participants with cSCI and able-bodied participants. If this brief isometric hand exercise cannot lead to significantly increased MEPs in participants with cSCI, our next step might test RIC in combination with more advanced interventions such as non-invasive paired stimulation, a technique that our research team is actively studying in other protocols. Finally, if the pilot study shows a significant synergistic effect of RIC on the isometric hand exercise task, our future goal will be coupling RIC with more prolonged rehabilitation training to promote long-term effects.

[figure not shown]

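### Aim 1 seeks synergy between RIC and exercise, but the plan does not name the RIC-by-time interaction, or any contrast, as the test of it

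*Combined protocol and SAP*

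**What the plan says.** The Overview describes a two-session crossover of active and sham RIC, and "The isometric hand exercise will be performed in both sessions". MEPs are measured at baseline, after RIC, immediately after exercise and 15 minutes later.

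Hypothesis 1A has two parts. MEP amplitude "will significantly increase after active RIC plus isometric hand exercise compared to sham RIC plus isometric hand exercise", and "Active RIC alone will not significantly increase motor evoked potential amplitudes". Hypothesis 1B has the same form for the secondary outcomes. No equivalence margin accompanies the second part.

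The Aim 1 rationale expects larger MEPs after exercise "due to the synergistic effects of active RIC on isometric hand exercise compared to sham RIC". The Aim 1 Potential Pitfalls paragraph moves on to prolonged training "if the pilot study shows a significant synergistic effect of RIC on the isometric hand exercise task".

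The Aim 1 Data Analysis section expresses each later value as percent change from the session baseline. The Statistical Analysis section plans a group (2) by RIC (2) by time (3) mixed ANOVA, with post-RIC as one of the three times. Bonferroni-adjusted pairwise tests follow if any main or interaction effect is found. Wilcoxon signed rank tests replace the ANOVA if its assumptions fail. No sentence says which result would establish synergy.

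**The concern.** An active-sham difference after exercise is the RIC effect at that time. It becomes evidence of synergy only if it is larger than the active-sham difference before exercise. Finding one difference significant and the other not does not show this: with 16 people, two equal effects can easily fall on opposite sides of the threshold.

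The plan's structure does not prevent that reading:
- A RIC main effect alone is enough to open the pairwise tests.
- The RIC-by-time F test has 2 degrees of freedom and no direction, so it can also be significant because the two post-exercise points differ from each other.
- Under the Wilcoxon fallback, no test of the interaction is described.

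At stake is the study's central interpretive claim. An additive RIC effect, or one that develops slowly, could be reported as synergy and used to justify the next study.

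**Working it through.** The documents give no effect size, SD, correlation, alpha or power, so there is no planned figure to reproduce. The check asks how often a RIC effect with no synergy yields the pattern in Hypothesis 1A.

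**Inputs from the plan.** n = 8 + 8 = 16 (Overview), a within-person active-sham comparison, and three post-baseline times.

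**Assumptions.** Two-sided alpha is 0.05. Groups are pooled, with no dropout. RIC alone is judged by the active-sham difference at post-RIC. Each participant has three active-sham differences with the same mean d (in SDs of that difference), unit SD and common correlation rho. Positive rho is plausible because all three share the same session baselines. The ranges are d = 0.3-0.7 and rho = 0.5-0.7, with 40,000 simulated trials per setting.

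**Tests.** Each is a paired t = mean / (SD/√16), with critical value 2.131 on 15 df.
- Pattern: the mean of the two post-exercise differences is significantly positive, and the post-RIC difference is not.
- Bonferroni pattern: either post-exercise point is significantly positive at 0.05/3, and post-RIC is not.
- Direct contrast: C = (mean post-exercise active-sham) − (post-RIC active-sham). Its true value here is zero.

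| d | rho | Post-exercise significant | Pattern | Bonferroni pattern, either point | C significant, favourable |
|---|---|---|---|---|---|
| 0.3 | 0.5 | 25.5% | 14.5% | 12.3% | 2.6% |
| 0.5 | 0.5 | 57.7% | 22.0% | 23.3% | 2.6% |
| 0.7 | 0.5 | 85.5% | 17.2% | 25.6% | 2.5% |
| 0.3 | 0.7 | 22.6% | 10.0% | 9.3% | 2.5% |
| 0.5 | 0.7 | 52.4% | 15.3% | 17.8% | 2.5% |
| 0.7 | 0.7 | 81.1% | 12.2% | 20.0% | 2.4% |

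**Plausibility check.** For two independent tests, each with power p, the pattern has probability p(1−p), at most 25%. At d = 0.5 the power at one time point is about 0.46, giving 0.46 × 0.54 = 0.25. Positive correlation lowers this, as the table shows.

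**Sensitivity.** At d = 0.9 the pattern falls to 5-7%. With no RIC effect it is about 2%. At rho = 0.3 it is 19-29% for d = 0.3-0.7.

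**If the interaction is also required.** The pattern together with a significant 2-df RIC-by-time test occurs in about 1% of these no-synergy trials (0.8-1.6%).

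**Precision of C.** Var(C) = (1+rho)/2 + 1 − 2·rho = 1.5(1−rho), so the SD is 0.87 at rho = 0.5 and 0.67 at rho = 0.7. The 95% half-width is 2.131 × SD/4, or 0.46 and 0.36. For a true added effect of 0.5 SD, power is about 58% and 79%; for 0.7 SD, about 86% and 97%.

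**Scale.** Suppose, as an illustration, that RIC multiplies the MEP by 1.2 and exercise multiplies it by 1.5, with no interplay. Before exercise the active-sham gap is 20 − 0 = 20 points. After exercise it is (1.2 × 1.5 − 1) − (1.5 − 1) = 80% − 50% = 30 points. The percent-change contrast is therefore +10 points, while the log-ratio contrast is ln 1.2 − ln 1.2 = 0.

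**The case against.** A reader might infer that the plan will claim synergy from the significant/non-significant pattern, and that 10-22% is therefore its false-synergy rate. The documents do not support either inference. Hypothesis 1A lists two predictions and does not say that together they establish synergy. The rationale states an expectation, and the Potential Pitfalls paragraph leaves open how a synergistic effect would be judged. The planned ANOVA already contains RIC-by-time, and an analyst who required it would rarely be misled (about 1% above). Its 2-df form costs some power rather than error control: for a true added effect of 0.7 SD its power is 74-93%, against 86-97% for the single contrast.

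The 23-86% rate of post-exercise significance is not an error rate either. It is the power to detect a real RIC effect, which Aim 1 legitimately seeks. It misleads only if relabelled synergy. The study is also a proof of concept, and it calls its own primary hypothesis highly speculative.

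These points narrow the concern without removing it. The interaction is present but has no designated role, a main effect alone opens the pairwise tests, the fallback omits the interaction, and nothing supports reading non-significance of RIC alone as absence of effect.

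Naming a contrast also has a limit. With exercise in both sessions, a RIC effect that grows with time would pass the contrast just as synergy would. That is a feature of the design and no analysis of these data can remove it.

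**Conclusion.** The concern holds in a limited form. The plan includes a suitable interaction term but does not designate it as the test of synergy, while its hypotheses and rationale invite judging synergy from separate significance statements. For an analyst who took that route and ignored the interaction, a constant RIC effect would show the pattern in about 10-22% of trials (9-26% with Bonferroni and either post-exercise point), against about 2.5% in the favourable direction for a direct contrast. These figures rest on the assumed effect sizes, correlations and pooling of 16 participants. They are not properties of the ANOVA as planned. The point should be settled before analysis because it governs the main claim, but it does not affect assignment or data collection.

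**What to change.** In the Aim 1 Statistical Analysis section:
1. Name one synergy contrast: (active minus sham, mean of the two post-exercise points) minus (active minus sham at post-RIC). Report it with a 95% CI.
2. If the ANOVA assumptions fail, apply the Wilcoxon signed rank test to each participant's value of that contrast.
3. State the scale on which no synergy is defined. Keep percent change if preferred, but also report the contrast on the log-ratio scale as a check, because purely multiplicative effects appear as synergy on the percent scale.
4. Do not treat non-significance of RIC alone as evidence of no effect; report its estimate and CI.
5. Reserve the word synergistic for the named contrast. Otherwise describe the result as RIC before exercise versus sham before exercise.
6. State as a limitation that a delayed RIC effect cannot be separated from synergy, because both sessions include exercise.

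The cost is a few sentences and one contrast from data already collected, with no new visits. The downside is a more modest claim and limited precision: with 16 participants the interval is roughly ±0.36 to ±0.46 SD under the assumptions above.

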The optimal scalp location for APB will be determined at the screening session and stored in our Brainsight TMS Navigation system (Rogue Resolutions) for later use in each experimental session. After navigating to the optimal stimulation spot, the RMT, used for calculating single- and paired-pulse stimulation of the APB will be determined by the lowest TMS intensity at which an MEP could be induced with at least 5 of the 10 stimuli with peak to peak amplitude of 50-100 μ V at rest. The single-pulse TMS will be applied at 120% RMT to induce and record peak-to-peak amplitude of MEP₁₂₀.

Cortical inhibition and facilitation: Paired-pulse TMS will be used to measure short interval cortical inhibition (SICI), long interval cortical inhibition (LICI) and intra-cortical facilitation (ICF)⁵⁰. Paired-pulse TMS includes a conditioning (CS) and test stimulus (TS) separated by a specified interstimulus intervals (ISI). The configuration for measuring SICI, LICI and ICF in this study are as follows⁵¹⁻⁵⁴:

- SICI: CS = 90% RMT, TS = 120% RMT, ISI = 3 ms
- LICI: CS = 120% RMT, TS = 120% RMT, ISI = 100 ms
- ICF: CS = 90% RMT, TS = 120% RMT, ISI = 12 ms

Peripheral Nerve Profile: Supramaximal electrical stimulation will be delivered at median and ulnar nerves at wrist level. The peripheral nerve profile includes the latency and the peak-to-peak amplitude of the M/F waves. The peak-to-peak amplitude of the M waves will be used to normalize the MEP₁₂₀ at each time point to ensure that changes of corticospinal excitability are not due to peripheral variation⁵⁰.

Data Analysis:

Corticospinal Excitability: The primary outcome will be MEP₁₂₀ on APB (primary outcome muscle) and FDI muscles. The MEP₁₂₀ will be first normalized to peak-to-peak amplitude of M waves to take account of the peripheral variation. The changes of MEP₁₂₀ at post-RIC, post-RICx-0 and post-RICx-15 will be expressed as percentage of the changes compared to baseline MEP₁₂₀. The SICI, LICI and ICF will also be expressed as percentage of the changes compared to baseline in each value.

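### Aims 1 and 2: the signed-rank fallback cannot compare cSCI with able-bodied participants; Aim 1: unadjusted percent change can cost power and inflate the group main effect

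*Combined protocol and SAP*

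**What the plan says.** **Fallback.** The Statistical Analysis paragraph of Aim 1 and the corresponding paragraph of Aim 2 each specify a mixed ANOVA with group (cSCI, able-bodied) as a factor. Both then say: "If the data is not normally distributed and the assumptions of the ANOVA are not met, Wilcoxon signed rank tests will be used instead". Neither names another test. The only stated check before the switch is in Aim 1: "Descriptive analysis will be computed first for all outcomes variables to test the distribution of the data". No test or threshold is given.

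**Group hypotheses.** Hypotheses 1A and 1B both end: "These trends will be similar in both cSCI and able-bodied participants". Hypothesis 2B says the same of inflammatory mediators. Hypothesis 1A also states: "Active RIC alone will not significantly increase motor evoked potential amplitudes".

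**Outcome scale.** Under Aim 1, Data Analysis, changes in M-wave-normalised MEP120 "at post-RIC, post-RICx-0 and post-RICx-15 will be expressed as percentage of the changes compared to baseline". For the paired-pulse measures: "The SICI, LICI and ICF will also be expressed as percentage of the changes compared to baseline in each value". The model is then: "A three way 2 (cSCI, able-bodied) by 2 (RIC, sham) by 3 (post-RIC, post-RICx-0, post-RICx-15) mixed-ANOVA will be used to analyze" these outcomes. Baseline is not a time level in that model, and no covariate is named. The Overview states: "Participants will be randomly assigned the order of the two experimental sessions: active or sham RIC".

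**The concern.** Group is a between-participant factor. A signed-rank test works on differences within a pair, and no pair links a cSCI participant to a control. Once the switch is made, the plan can still say whether active RIC differs from sham, but it has no method for saying whether the two groups respond alike. Three of its hypotheses include that claim.

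The outcome scale raises a separate and smaller question. Dividing by one noisy session baseline carries that noise into every post value. A covariate could remove part of it, using data the trial already collects. The division also shifts mean percent change upward by an amount that grows with the noise, so a noisier group can look as if it responds more.

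**Working it through.** The documents give no power, SD, effect size or baseline-to-post correlation, so there is no figure of theirs to reproduce. From the documents: 8 cSCI and 8 able-bodied participants, two sessions each, one baseline and three post times per session. **Assumed:** lognormal MEP/M-wave, between-subject log SD 0.8, true +50% under active RIC after exercise, two-sided 5%. Triplets are occasion log SD σ = 0.3/0.45/0.6; τ is the session log SD.

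**Part 1: the fallback**

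What the signed-rank test can reach follows from the text alone:

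| Question | Comparison | Signed-rank usable? |
|---|---|---|
| Active vs sham (1A, 1B); Hypothesis 2A | within participant | yes |
| Condition by time | within participant | yes |
| Similar in both groups (1A, 1B, 2B) | 8 people vs 8 others | no |
| Aim 3 | groups analysed separately | yes |

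Two workarounds fail:

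- *Pairing across groups.* The result depends on arbitrary pairs. On one simulated data set the signed-rank p-value ran from 0.20 to 1.00 across pairings; rank-sum gave 0.44.
- *One test per group.* With n=8, significance needs W≤3 (p=0.039). With the same true +50% in both groups, exactly one group is significant in 43/27/19% of trials at a single time point (τ=0.3).

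Rank-sum 8 vs 8 (U≤13, p=0.0499) rejects in about 5% when the groups are alike. It is weak, though: with +50% in one group and none in the other it rejects in 29/16/11%, even on the mean of the two post-exercise times.

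Hence the interval. At one post time, a participant's log contrast (active change minus sham change) has variance 4σ², so SD 2σ. The 95% half-width between groups is 2.145 × 2σ × √(2/8) = 2.145σ, that is 0.64/0.97/1.29, or a factor of 1.90/2.63/3.62 each way. At the lowest noise, an estimated ratio of 1.0 runs from 0.53 to 1.90, which still includes 1.5.

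For 2B, the Aim 2 model keeps baseline versus post-RIC as a factor, so the group question is group × condition × time. With an assumed true group difference of 1 Ct, the baseline-to-post contrast estimates 1 Ct. Averaging over baseline and post gives (0+1)/2 = 0.5 Ct. At assumed Ct occasion SD 0.2/0.3/0.5, rank-sum power is 99/85/44% against 49/42/28%.

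**Part 2: the outcome scale**

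*Level.* With no effect, active versus sham on percent change rejects in 3.9–5.1%; the log regression with baseline covariate rejects in 4.6–5.2%.

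*Power.* Let ρ = τ²/(τ²+σ²), the baseline-to-post correlation within participant. The variance ratio of adjusted to change analysis is (1−ρ²)/[2(1−ρ)] = (1+ρ)/2.

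- τ=0.3: ρ = 0.50/0.31/0.20, ratio 0.75/0.65/0.60. Simulated power at one post-exercise time, before Bonferroni: percent change 65/33/17%, adjusted log 78/51/32%, a gain of 13/18/15 points.
- τ=0.9: ρ = 0.90/0.80/0.69, ratio 0.95/0.90/0.85. The gain is about 2 to 8 points.

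Repeat runs agree to within about 3 points. SICI, LICI and ICF were not simulated.

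*Group main effect.* With no true effect, log(post/baseline) has variance 2σ², so mean percent change is exp(σ²)−1. At σ=0.3 that is exp(0.09)−1 = 9.4%; at σ=0.6 it is exp(0.36)−1 = 43.3%. If cSCI values are about twice as variable, the group main effect on percent change rejects in about 10–14% of null trials, against 5–6% on logs. A calculation with one post time and smaller noise gave 6–8%.

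*Which times.* If facilitation is present at post-RICx-0 only, the baseline-adjusted mean of the two post-exercise times has 39% power (σ=τ=0.3). Plain percent change at post-RICx-0 alone has 65%.

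**The case against.** **Matching could supply the pairs.** Controls are age-matched within 5 years, and the Project timeline expects one SCI participant and one control every two months. If matching were one-to-one, a signed-rank test on matched pairs would be possible. But no pairs or paired group analysis are described, and Aim 2 calls group a between-group factor. Matching does not close the gap.

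**The gap is conditional.** It opens only if the switch is made, and its frequency cannot be computed because no trigger is defined. That stands. The switch is nonetheless a planned route, and Aim 1's pitfalls paragraph itself expects wide variability in cSCI.

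**Similarity is an expectation, not a significance claim, and the study is preliminary.** This is fair, and it has a consequence: a non-significant ANOVA interaction would not show similarity either. The interval therefore belongs in the main analysis as well as the fallback.

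**Part 2 rests on assumed inputs.** That also stands. The gain is small when session variation dominates, so it is an improvement, not the correction of an error. The plan's condition-by-time term and Bonferroni comparisons already reach individual times, and Aim 1 describes post-exercise facilitation as short-lived. Averaging post-RICx-0 with post-RICx-15 could therefore do harm.

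**Conclusion.** **The fallback is wrong as written and should be fixed.** That follows from the text without any assumed figure. The gap is confined to the between-group parts of Hypotheses 1A, 1B and 2B. A reader might infer that Aims 1 and 2 lose their analysis altogether once the switch is made. They do not: the within-participant questions, including Hypothesis 2A, remain testable by signed-rank.

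**The outcome scale is a cheap improvement.** A reader might infer that percent change invalidates the primary active-versus-sham test. It does not: null rejection stays near 5%. The cost is about 2 to 18 points of power per time point under the assumed log SDs, and its size depends on a correlation the documents do not give. The assurance does not extend to the group main effect, which can reach about 10–14% null rejection if cSCI values are about twice as variable. That variability ratio is also an assumption.

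**What to change.** **Fallback, Aims 1 and 2.** Keep signed-rank for within-participant contrasts. Between groups, add a rank-sum or permutation test on:

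- each participant's active-minus-sham contrast at each of post-RIC, post-RICx-0 and post-RICx-15, for 1A and 1B;
- the active-minus-sham difference in baseline-to-post change, for 2B.

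State the check that triggers the switch.

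**Main analysis and fallback.** Report each between-group difference with a 95% interval (Hodges-Lehmann in the fallback, for example). Do not read a non-significant result as similarity.

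**Aim 1 scale (improvement).** At each post time, regress the active-minus-sham difference in log(MEP120/M-wave) on the active-minus-sham baseline difference, with centred group and sequence terms. Keep the planned Bonferroni adjustment, and do not use the mean of the two post-exercise times. Test any group main effect on the unadjusted log ratio. SICI, LICI and ICF can be treated the same way once expressed as positive ratios.

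**Cost.** SAP wording only. Results become geometric-mean ratios. Two degrees of freedom are spent, a loss of a few points of power at most when session variation is large. Near-zero values need a pre-stated floor before logs are taken.

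### Averaging percent change from a single session baseline overstates the MEP increase when nothing has changed; the log ratio removes the bias at almost no cost

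*Combined protocol and SAP*

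**What the plan says.** The study is a two-session crossover (Approach, Overview): "We propose a randomized crossover study to compare active versus sham RIC combined with one bout of isometric hand exercise". There are 8 participants with cSCI and 8 able-bodied controls. The baseline is a single pre-test in each session: "Each session will consist of a pre-test measurement (baseline), active/sham RIC, post-RIC measurement", followed by the exercise and the post-exercise readings.

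Under Aim 1, Data Analysis, MEP120 is divided by the M wave. Its changes at the three post times "will be expressed as percentage of the changes compared to baseline". SICI, LICI and ICF are treated the same way.

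Under Aim 1, Statistical Analysis, these values enter a group (2) by condition (2) by time (3) mixed ANOVA. The time factor holds only the three post readings, so baseline acts as the divisor and is neither a level nor a covariate. The fallback is a Wilcoxon signed rank test. No transformation and no number of averaged pulses is given. The same section announces that "Electrophysiological outcomes will be compared after RIC and after the isometric hand exercise relative to baseline values", but names no test of change against zero.

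Hypothesis 1A concerns active versus sham and adds: "These trends will be similar in both cSCI and able-bodied participants".

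**The concern.** A ratio with a noisy denominator does not average to 1 when numerator and denominator have the same true value. Low baseline readings inflate the ratio more than high ones deflate it. A mean percent change of zero is therefore not the no-change state on this scale, and equal mean percent change in two groups is not the same as equal response unless their noise is equal.

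Three uses of the results are exposed:
- **Size of the increase.** The figure a pilot passes on to later studies is too large.
- **Readings against baseline.** The plan compares outcomes with baseline in general terms. Its Potential Pitfalls text also links a possible next step to whether the exercise significantly raises MEPs in cSCI.
- **Group main effect.** It is one of the effects that opens post hoc comparisons, and it could be read as bearing on whether the groups respond alike.

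**Working it through.** **Inputs from the documents.** 8 + 8 participants, 2 sessions, 1 baseline and 3 post readings per session, percent change from the session baseline. The plan states no MEP variability, alpha or power for Aim 1, so there is no figure of its own to reproduce.

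**Assumptions.** No true change; proportional lognormal noise, independent between readings, with CV as shown; two-sided 5% tests. Noise shared by baseline and post readings cancels in the ratio, so CV means the independent part only.

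**Bias.** Write post = m·e1 and base = m·e0, with e0 and e1 independent, mean 1, and log variance s² = ln(1 + CV²). Then E[e1] = 1 and E[1/e0] = exp(s²) = 1 + CV², so

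E[post/base] − 1 = CV².

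- CV 20%: 0.20² = +4%
- CV 30%: 0.30² = +9%
- CV 40%: 0.40² = +16%
- CV 50%: 0.50² = +25%

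Gamma noise gives CV²/(1 − CV²), which is somewhat more: 0.25/0.75 = +33% at CV 50%.

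**False rejection, equal noise in both groups** (simulation, at least 20,000 null trials per setting). The increase is each participant's mean over both sessions and all three post times, tested against zero by one-sample t. The group main effect of the balanced ANOVA equals a pooled t-test on the same participant means.

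| CV | Increase, all 16 | Increase, 8 cSCI | Group main effect |
|---|---|---|---|
| 20% | 12% | 7% | about 5% |
| 30% | 20% | 9% | about 5% |
| 50% | 41% | 15% | about 5% |

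**False rejection, unequal noise** (able-bodied CV 20%).

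| cSCI CV | Spurious group gap in mean percent change | Group main effect |
|---|---|---|
| 30% | 9 − 4 = 5 points | 6% |
| 40% | 16 − 4 = 12 points | 9% |
| 50% | 25 − 4 = 21 points | 13% |

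Nearly all the excess is in the direction cSCI above able-bodied. At CV pairs 20/40, 30/50 and 20/60%, adding real participant-level variation in response (log SD 0.2 to 0.3) gives 6.6% to 14.4%.

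**Not inflated in the same simulations.**
- Active versus sham: 2.6% to 5.3%.
- Group by condition: 4.9% to 5.7%.
- 8 cSCI, one session, one time: 4.5% to 5.1%.
- 8 cSCI, one session, both post-exercise times averaged: 5.0% to 5.9%.

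In the last two the estimate is still biased upward, but skew at n = 8 offsets the bias in the test.

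**Wilcoxon fallback.** On the averaged increase, at CV pairs 20/40, 30/50 and 20/60%, it rejects in 17% to 23% (all 16) and 11% to 16% (8 cSCI), so it does not cure the problem.

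**Log ratio, same settings.** The null mean is 0 whatever the CV. The averaged increase in all 16 rejects in 4.3% to 5.5%; the group effect in 4.7% to 5.2% with equal noise and 5.0% to 6.7% with unequal noise.

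**The case against.** The strongest reply is that the primary hypothesis is untouched. Both sessions carry the same expected offset, so it cancels in active versus sham. The similarity claim in Hypothesis 1A follows statements about active versus sham and about active RIC alone; for the former, the matching term is group by condition, which is also centred on zero. This stands. A reader might infer that the percent-change scale undermines the trial's main result; the design does not support that.

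Second, the inflated test against zero is not written into the plan. The ANOVA has no baseline level, and pooling over sessions and times mixes in the reading taken before the exercise. This also stands in part. Exposure rests on the general baseline wording and the remark about MEPs in cSCI. A reader might conclude that any increase from baseline is spurious, but within one session in 8 participants the rejection rate stays near nominal. Nor is the rate in 8 cSCI double at CV 20%: that comes from counting the upper tail alone (about 6% against 2.5%), whereas two-sided it is about 7% against 5%.

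Third, a noisier cSCI baseline is assumed. The plan's remark that injury level and residual circuits "might result in the wide variability of the outcomes" concerns differences among participants, not error within a session. The stored stimulation site, threshold-scaled intensity and choice of the arm with consistent responses all work towards low noise. This stands; with equal noise the group test is nominal.

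What the reply does not remove is the bias in the reported mean, which needs no group difference and no particular test. More participants do not shrink it. More averaged baseline pulses do shrink the pulse-to-pulse part, but the plan states no number.

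**Conclusion.** The concern holds in limited form. Mean percent change from a single session baseline is biased upward by about CV² under no change: 4 to 25 percentage points for assumed CVs of 20% to 50%. Increases averaged over sessions and times reject too often, at about 12% to 20% in all 16 participants and 7% to 9% in the 8 with cSCI for CV 20% to 30%. The group main effect is biased only if noise differs between groups, and then modestly: about 6% to 13% over the range tabulated.

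Every figure depends on an assumed CV and on noise independent between readings, neither of which the documents supply. The active-versus-sham and group-by-condition tests are sound in this respect. For SICI, LICI and ICF the direction is expected to be the same, but the plan does not define how those values are computed and they were not simulated. This is a worthwhile improvement to the analysis scale, not a flaw in the primary comparison.

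**What to change.** In Aim 1, Data Analysis, make the analysed value

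d = ln(MEP120/M at the time point) − ln(MEP120/M at that session's baseline).

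Run the planned group by condition by time model on d, then report means and confidence limits as 100 × (exp(d) − 1). Do not give arithmetic means of individual percent changes as the size of the increase. State how many pulses are averaged per reading. Apply the same scale to SICI, LICI and ICF only where values are positive and not near zero, and fix any floor value before the data are seen.

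**Cost.** One or two sentences of wording; no new data, visits or participants. The estimate becomes a geometric-mean percent change, usually smaller than the arithmetic mean. Amplitudes near zero need the pre-set floor, and for strongly inhibited responses the result can depend heavily on it. The primary contrast loses little or nothing: in checks with illustrative true effects, power on the percent and log scales was 43% versus 42%, 29% versus 31%, 67% versus 70%, and 46% versus 54%.
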